7.2 Methods and Timing for Assessing, Recording, and Analyzing Safety Parameters

Reports of our safety measures will be delivered to our Data Safety Monitoring Board.

7.3 Adverse Events

Per CDC guideline clarification, adverse events are defined as an abrupt discontinuation of opioids for persons whose most recent prescription exceeds > 49 morphine equivalent daily dose; or as reported to study staff. ([Dowell et al. 2019](#)) Emergency department visits will also be evaluated as well as *increases* in prescribing $> 20\%$ presumably in response to reports of worsening pain.

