5.2 Handling of Study Interventions

The following interventions will be tested: *Accountable Justification (AJ)* is an EHR-based intervention that will prompt the clinician to justify, in a free text response, the decision to prescribe an opioid or to not reduce high risk/high dose prescribing. The prompt is designed to inform the clinician that the justification will be seen by others in the patient's medical record as an "High risk prescribing justification" note, and that if no justification is entered, the phrase "no justification given" will appear in the note.

Delivery of AJ nudges in Epic's electronic health record (EHR) based on patient type is described below.

Opioid-naïve: An automated search of EHR data determines whether the patient received an opioid prescription within 90 days. If no opioid was prescribed, the clinician receives an alert cautioning against initiating a prescription based on current guidelines. The clinician can either remove or continue with the current opioid prescription. The former results in return to normal workflow after receiving a prompt recommending physical therapy and non-opioid alternatives. The latter, however, induces a prompt requiring the clinician to justify their decision in free text. A Justification Note with the clinician's response is recorded in the Visit Summary portion of the patient's record. A generic "No justification given" is generated for blank responses.

At-risk for long term use: If an automated search of EHR data reveals an opioid prescription(s) within 90 days of the current order, but no previous opioid prescription prior to 90 days before, a prompt explaining the danger of continuing refills based on current guidelines appears. The process is otherwise the same as above; clinicians who cancel a prescription receive a prompt recommending non-opioid alternatives and physical therapy, whereas those who continue with the order are required to justify their decision.

Long term opioid recipient: If an automated search of EHR data reveals total opioid doses are at least 50 MME per day, there are two or more prior opioid prescriptions with two different start dates both greater than 1 day and less than 91 days, and there is a prior opioid prescription with a start date greater than 90 days and less than 181 days, a prompt suggesting an opioid taper appears.

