7. SAFETY ASSESSMENTS

Data for patients who were noted to have been abruptly stopped of opioid prescriptions, emergency room eligible study visit with a diagnosis that could represent a serious complication of untreated pain will be extracted from study site EHRs and reported to the Data Safety and Monitoring Board. Relative rate of ED visits between study conditions will also be evaluated.

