7.1 Specification of Safety Parameters

Data elements from qualifying visits for providers enrolled in the study will be collected from the electronic health record. Clinics will incorporate exclusions (ICD 10 cancer suppressor codes found [here](#)) used in the decision to trigger the clinical decision support. Aggregate counts of total visits across sites for which the intervention was triggered, for high dose opioid patients, if abrupt changes to dose ($> 20\%$ morphine equivalent daily dose) were made. Such cases will be examined closely to determine if unsafe drops in opioids occurred.

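### The dose-based discontinuation event in 7.3 is read on the most recent prescription, so a patient lowered below the cut after a taper prompt and then stopped can fall outside both the 7.3 and 7.1 counts

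*Combined protocol and SAP*

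**What the plan says.** Five statements in the combined protocol and SAP bear on this point.

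- **Prompt (5.2, same category in the Précis and 9.1).** A patient with the required prescription history is a long-term recipient when "total opioid doses are at least 50 MME per day". At that point "a prompt suggesting an opioid taper appears".
- **Adverse event (7.3).** The dose-based definition is "abrupt discontinuation of opioids for persons whose most recent prescription exceeds > 49 morphine equivalent daily dose". A second route follows: "or as reported to study staff". Emergency department visits are also evaluated.
- **Dose-change count (7.1).** The plan specifies "Aggregate counts of total visits across sites for which the intervention was triggered, for high dose opioid patients, if abrupt changes to dose" above 20% of the daily dose were made, and adds: "Such cases will be examined closely to determine if unsafe drops in opioids occurred".
- **Extraction for the DSMB (section 7).** "Data for patients who were noted to have been abruptly stopped of opioid prescriptions" will be extracted and reported. The sentence is hard to parse. It gives no dose threshold and no rule for what counts as abrupt.
- **Timing (6.1).** Adverse events are scheduled from intervention start onward, and ordering data are collected throughout.

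No section says at what date the most recent prescription is read, or links the event to the dose at the prompt.

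**The concern.** For whole-number doses, the cut that brings a patient under the taper prompt and the cut that makes a stop an adverse event are the same. The prompt is meant to bring about dose reductions. If the event is judged on the last prescription before the stop, a reduction that follows the prompt can move the patient out of the event definition shortly before the stop that the safety review should see.

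Any resulting undercount leans towards no harm, and it can grow as more patients respond to the prompt. The DSMB receives these safety measures (7.2) and may recommend discontinuation on safety grounds (9.3). The pilot has one clinic and no randomization (9.2), so no control arm would reveal the undercount.

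**Working it through.** The plan gives no event rate, sample size or dose distribution for this point, so there is no figure of its own to reproduce. The check applies its rules to illustrative dose paths for a long-term recipient on one opioid.

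**Rules**
- Prompt dose condition (5.2): total ≥ 50 MME/day.
- 7.1 flag: change > 20%, read here as the change from one order to the next, at a visit where the intervention was triggered.
- 7.3 dose-based event: abrupt stop with the most recent prescription > 49, read here as the last prescription before the stop.

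**Step 1. Direct stop.** From 50, 55, 60 or 90 MME/day the last prescription exceeds 49, so 7.3 is met. The definition works when nothing comes between prompt and stop.

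**Step 2. One reduction, then a stop.** Cut = (start − lowered dose)/start.

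| Path | First cut | 7.1 flag on the cut | 7.3 event at the stop |
|---|---|---|---|
| 50 → 49 → 0 | 1/50 = 2.0% | no | no |
| 55 → 45 → 0 | 10/55 = 18.2% | no | no |
| 60 → 48 → 0 | 12/60 = 20.0% | no (not above 20%) | no |
| 62 → 49 → 0 | 13/62 = 21.0% | yes | no |
| 90 → 45 → 0 | 45/90 = 50.0% | yes | no |

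**Step 3. Range of starts.** The highest start from which one unflagged step reaches 49 solves S × 0.80 = 49, so S = 49/0.80 = 61.25. Every start from 50 to 61.25 MME/day allows the two-order path. Above that, a single cut to 49 or less is flagged under 7.1, although the later stop is still not a 7.3 dose-based event. Repeated 20% steps avoid the flag from higher doses: 90 → 72 → 57.6 → 46.1, then a stop.

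**Step 4. Does 7.1 catch the later stop?** It counts visits where the intervention was triggered. A long-term recipient now at 48 fits none of the three prompt categories. The long-term category needs at least 50. The naïve category needs no prescription within the prior 90 days, and the at-risk category needs none from before that window. Section 1.1 also says prompts appear at the time of prescribing, so a stop made by writing no order is not a triggered visit.

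**Step 5. Quantity measured.** The prompt reads the total dose and 7.3 reads the most recent prescription. Two concurrent prescriptions of 30 MME/day total 60, which meets the prompt's dose condition. The most recent prescription is 30, which does not meet the 7.3 condition. This second mismatch needs no reduction at all.

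**The case against.** The strongest reply is that such stops are not invisible. Section 7 promises the DSMB data on abruptly stopped patients with no dose threshold, 7.3 also admits events reported to study staff, and emergency department visits are evaluated. This stands. A reader might infer from the dose paths that these stops are never counted, and the documents do not support that. However, the section 7 extraction has no operational definition, staff reports are passive, and 7.3 is the only place that defines the adverse event.

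A second reply is that the reference dates are unstated. Perhaps high-dose status under 7.1 is fixed when the prompt fires, and perhaps the most recent prescription is not the lowered one. It is true that no date is given, so the reading used here is the plain one and not the only one. For 7.1 the reply does not go far enough, because the count is tied to triggered visits and the later stop is not at one (step 4).

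Third, 5.2 suggests a taper but sets no target below 50. A reader might infer that getting under the cut is the nudge's stated aim, but no section says so. It is enough that a reduction from just above 50 can cross the cut.

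Finally, this is a single-clinic feasibility pilot with DSMB oversight, case review and no planned test of the 7.3 count. That limits the consequences but does not repair the count.

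**Conclusion.** The concern holds in a limited form. The 7.3 dose-based count and the 7.1 dose-change count can understate stops that follow a reduction prompted by the intervention. Stops from any start of 50 to 61.25 MME/day can escape both through one intermediate order, and from higher starts through several. This rests on reading the most recent prescription as the last one before the stop, and the 20% limit as applying order by order.

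The number of missed events cannot be computed, because the documents give neither a dose distribution nor the frequency of such sequences. One could assume that doses above 50 have an exponential excess with mean m of 20, 40 or 60 MME. The share of patients starting at or below 61.25 is then 1 − exp(−11.25/m) = 43%, 25% or 17%. A reader might take these as rates of missed events. They are only the shares whose starting dose permits the one-step path, under a distribution the documents do not supply.

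A bias in a before-and-after comparison of adverse events should not be inferred either, since 6.1 schedules adverse events only from intervention start.

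**What to change.** For event counting only:

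1. Once a patient has triggered the long-term prompt, keep that patient in the abrupt-stop count and the > 20% change count for the rest of the intervention period, whatever the later dose.
2. Report these stops to the DSMB alongside the 7.3 count as now defined, so that both can be seen.
3. Reconcile sections 7, 7.1 and 7.3 on which dose identifies the at-risk patient: at the prompt or most recent, and total or single prescription. State the date at which it is read. The sponsor must settle that choice; none is proposed here.

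The numeric cut and patient care stay as they are.

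The cost is a change to the safety query, using ordering data already collected. The downside is that some planned, completed tapers will be flagged and will need the case review that 7.1 already provides.

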7.4 Reporting Procedures

The Principal Investigator will report any unanticipated events to the IRB as well as the Data Safety and Monitoring Board (DSMB) assembled for this study. When notified of an unanticipated event, the DSMB will convene and make a decision as to whether the study should continue. The IRB will also be notified of the DSMB's decision.

7.5 Safety Monitoring

A Data Safety and Monitoring Board (DSMB) has been established by NIH. The following individuals were recommended to NIH with expertise in either opioids, overprescribing or biostatistics/research methods: [name], [name], and [name].

8.

INTERVENTION DISCONTINUATION

Following each DSMB meeting, the board will make recommendations to the local IRBs as to whether the study should continue or if changes to the protocol are necessary for continuation.

9.

STATISTICAL CONSIDERATIONS

9.1 General Design Issues

Hypotheses

Our primary hypothesis is that clinicians receiving behavioral economic interventions will have lower opioid prescribing rates post-intervention as compared to baseline. We will estimate weekly milligram morphine equivalent for each clinician and observe the change each month. This will capture CDC guideline prescribing endpoints.

Design

The Application of Economics & Social psychology to improve Opioid Prescribing Safety (AESOPS) R21 is a pilot study to test the feasibility of clinical decision support nudges within the electronic health record to discourage unnecessary opioid prescribing through the application of "behavioral insights"— empirically-tested social and psychological interventions that affect choice. Over a 34 week study period, participating clinicians will receive any of three nudges when eligibility criteria are met within a patient's chart: 1) **Opioid naïve**: Visit where the order is for an included opioid and there is no prior opioid prescription with a start date of greater than 1 day and less than 91 days, 2) **At-risk for long term use**: Visit where the order is for an included opioid there is a prior opioid prescription with a start date greater than 1 day and less than 91 days, and there is no prior opioid prescription with a start date greater than 90 days, and 3) **Long-term opioid recipient**: Total opioid doses are at least 50 MME per day, there are two or more prior opioid prescriptions with two different start dates both greater than 1 day and less than 91 days, and there is a prior opioid prescription with a start date greater than 90 days and less than 181 days.

Outcome Measures

The primary outcome is change in weekly milligram morphine equivalent from baseline to post intervention period. We will estimate weekly milligram morphine equivalent for each clinician and observe the change each month. This will capture CDC guideline prescribing endpoints.

9.2 Sample Size and Randomization

Not applicable as this is a pilot feasibility study within one clinic with no randomization.

9.2.1 Treatment Assignment Procedures

Randomization of study sites

Not applicable as this is a pilot feasibility study within one clinic with no randomization.

9.3 Interim analyses and Stopping Rules

No interim analysis will be conducted on primary or secondary outcomes. The Data Safety and Monitoring Board is granted the power to recommend discontinuation of the study to each study IRB, if safety concerns are found.

9.4 Outcomes

9.4.1 Primary outcome

The primary outcome is change in weekly milligram morphine equivalent over 6 months. We will estimate weekly milligram morphine equivalent for each clinician and observe the change each month. This will capture CDC guideline prescribing endpoints.

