1.1 Primary Objective

The objective of the R21 pilot phase of the Application of Economics & Social psychology to improve Opioid Prescribing Safety (AESOPS) study is to develop and test novel behavioral nudges to encourage adherence to pain and CDC guidelines for opioid prescribing for persons with noncancer pain. At the time of opioid prescribing, clinicians will be prompted with an EHR nudge when the prescribing history for the patient falls into one of the following three mutually exclusive categories: Opioid naïve, At-risk for long term use, or Long-term opioid recipient. The primary outcome is average weekly morphine milligram equivalents (MME) prescribed per-clinician.

2. **BACKGROUND AND RATIONALE**

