2.1 Background on Condition, Disease, or Other Primary Study Focus

Over the last two decades, prescription opioids have grown to become a public health crisis. Today, on average 1 in 5 persons with chronic noncancer pain receives an opioid prescription in the U.S.¹ Yet, despite this record level of prescribing, reports of pain in America have not gone down.^{10,11} The greater availability of prescription opioids has been accompanied by alarming rise in the negative consequences related to their use. In 2015, there were over 365,000 emergency department visits for misuse and 20,101 prescription overdose deaths, more than have ever been recorded in U.S. history.⁵ The costs of prescription opioids are staggering. Aggregate costs for prescription opioid harms are estimated at over \$78.5 billion (in 2013 dollars). One-fourth of the aggregate economic burden is publicly funded (i.e., Medicaid, Medicare, and veterans' programs).^{12,13}

In 2016, the CDC issued the “CDC Guideline for Prescribing Opioids for Chronic Pain” which gives 12 patient care recommendations: (1) *use alternatives to opioids*, (2) *set realistic goals* for pain and function, (3) *discuss opioid risks* upon therapy initiation, (4) *use immediate release agents* instead of long-acting ones, (5) *use lowest effective starting dose, avoid escalation* above 50 milligram (mg) morphine equivalent (ME) daily dose and abide by a 90 mg ME/day dose prescribing limit, (6) *prescribe lowest dose at lowest quantity needed for acute pain*—usually 3 days with a maximum of 7 days in rare cases, (7) *evaluate for and discuss tapering* within 1 - 4 weeks and after 90 days, (8) *prescribe naloxone and evaluate substance use history* with opioid prescription, (9) *review the state prescription drug monitoring program data* (10) *conduct urine drug tests* to provide information about drug use that is not reported by the patient, (11) *avoid co-prescribing* with benzodiazepines, and (12) *refer patients with opioid use disorder to medication-assisted treatment in combination with behavioral therapies*. Our objective is to increase adherence to the CDC guideline and Oregon Pain Guidance pain management guideline. To evaluate the effects of doing so, we will measure as a primary outcomes clinician aggregate monthly mg ME

for patient visits with ≥ 50 mg ME daily dose. Secondary outcome is rate of dose escalation to ≥ 50 mg ME/day.

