2.2 Study Rationale

Rationale for Accountable Justifications. In the Accountable Justifications intervention, clinicians will be prompted to record an explicit justification for why they are prescribing an opioid that appears in the patient's EHR. Accountable justifications incorporate several behavioral principles. First, they signal an injunctive norm (a norm, often provided by an authoritative source, that strongly indicates how people should behave) indicating that prescribing an opioid is not recommended. This may make the clinician more likely to believe both that not prescribing an opioid is the best medical decision and that prescribing when it is not indicated violates professional standards. Second, it incorporates social accountability. A clinician justification become an explicit, separate part of the medical record, so a clinician's decision to prescribe is subject to the review and judgment of the provider's peers. Third, the justification alert implicitly designates guideline-concordant prescribing as the default action. Defaults are options that are exercised if the decision maker takes no special action to opt in or out of a given choice. Prior to our intervention, choosing to deviate from guidelines did not carry a special requirement to document a clinical rationale in the EHR. Accountable justifications, therefore, reset the default action. Guideline-concordant treatment choices will not require special justification, but a clinician must now "opt-in" to prescribing an opioid by providing a justification for which they are accountable.

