9.5 Data Analyses

For sample descriptive statistics, we will use means and medians for continuous measures, frequencies for count data, and standard deviations and interquartile ranges for variance. For inferential analysis, our primary hypothesis is that milligram morphine equivalent dose will decrease for persons on high doses of opioid therapy.

10. Statistical Analysis

Measures

The primary outcome is average weekly morphine milligram equivalents (MME) prescribed per-clinician. We assessed change in average per-clinician weekly MME from the 34-week baseline period before, to the 34-week period post-intervention using a mixed-effects, knotted spline, left censored regression to account for baseline differences in prescribing, a non-linear change in the rate of opioid prescribing from baseline to post-intervention, and an inflated number of weeks with an average MME of zero, respectively. Predictors include the fixed effects time in weeks, time with a knot at the intervention start, and a random intercept for clinician. The density function to achieve maximum likelihood estimates for a left censored regression is the observed probability of y_i assuming normal distribution ($x_i\beta, \sigma^2$) given that $y_i > 0$, weighted by the probability that y_i is above a censoring threshold, in this case zero.² Because uncensored observations are often skewed, we used log average weekly MME as our dependent variable. The percentage change in log MME per one unit increase in the uncensored, or latent variable was

measured using:

$$\log(MME)^* = \beta_0 + \beta_1 Time + \beta_2 (Time - t^*) + \zeta + error^1$$

where $\log(MME)^*$ is the latent, uncensored variable, time is the number of weeks, t^* is the spline knot for the intervention start, and ζ is the clinician random effect.¹ We adjusted the coefficients by calculating the average partial effect to interpret not just the linear change in $\log(MME^*)$, but the non-linear likelihood that $\log(MME^*)$ is uncensored, resulting in comparable estimates to ordinary least squares.²

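### Weekly MME per clinician is a prescribing-volume measure and cannot show whether the guideline's dose and duration limits were met, although sections 9.1 and 9.4.1 say that it captures guideline endpoints

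*Combined protocol and SAP*

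**What the plan says.** Section 9.4.1 defines the outcome: "The primary outcome is change in weekly milligram morphine equivalent over 6 months". It then adds: "This will capture CDC guideline prescribing endpoints". The same sentence stands twice in section 9.1, under Hypotheses and under Outcome Measures. Section 10 repeats the outcome as the quantity to be modelled, on the log scale: "The primary outcome is average weekly morphine milligram equivalents (MME) prescribed per-clinician". Neither definition has a daily-dose threshold, a days' supply or a restriction to a type of patient.

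Section 2.1 states the purpose: "Our objective is to increase adherence to the CDC guideline and Oregon Pain Guidance pain management guideline". It lists twelve recommendations. Those with numbers concern daily dose (avoid going above 50 mg ME, keep to a limit of 90 mg ME) and days for acute pain (usually 3, at most 7 in rare cases). Others, such as naloxone, checks of the monitoring program, urine tests and benzodiazepine co-prescribing, are not MME quantities.

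Section 2.1 ends with a different set of outcomes. Its primary is a clinician's monthly mg ME at visits with a daily dose of at least 50 mg ME, and its secondary is the rate of escalation to that dose. Section 9.5 frames the primary hypothesis as a decrease for people on high doses. Section 9.4.2 lists no secondary outcomes. Daily dose otherwise appears only in the trigger for long-term recipients (5.2) and in the safety sections (7.1, 7.3). No outcome anywhere uses days' supply.

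**The concern.** The sentence claims a property that the outcome does not have. Whether a dose or duration limit was met depends on the patient's daily dose and the number of days, each compared with a cut-off. Weekly MME adds up dose times days over all of a clinician's prescriptions, and after that sum neither factor can be recovered.

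A reader who accepts the sentence could take a fall in weekly MME as evidence that the section 2.1 limits were better kept, or take an unchanged total as evidence that they were not. Neither follows. The documents foresee a later cluster randomized trial of these nudges, so the label may be carried forward. The outcomes that would answer the dose question are already named in section 2.1, but they do not reach section 9.4 or the section 10 model.

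**Working it through.** The plan gives no sample size, power or effect size on this point, so there is no figure to reproduce. The check is an identity plus illustrations.

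**Inputs from the plan (section 2.1):** cut-offs of 50 and 90 mg ME/day, and 7 days for acute pain.

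**Assumed:** the order mixes below; one order per patient, so that the order's dose is the patient's total daily dose; weekly MME is the sum over a clinician's orders in that week. The plan does not spell out how the weekly average is formed.

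**Formula:** weekly MME = sum over orders of (MME/day × days).

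**1. Same total, different status on the limits.**

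| Orders | Total MME | At or above 50/day | Beyond 7 days |
|---|---|---|---|
| 10 × 30/day × 3 days | 900 | 0 of 10 | 0 of 10 |
| 1 × 90/day × 10 days | 900 | 1 of 1 | 1 of 1 |
| 1 × 30/day × 30 days | 900 | 0 of 1 | 1 of 1 |
| 3 × 100/day × 3 days | 900 | 3 of 3 | 0 of 3 |

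One value of the outcome fits all four combinations.

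**2. A fall in the total with no change at high dose.**
- Before: 20 × 30 × 3 + 2 × 60 × 30 = 1800 + 3600 = 5400.
- After: 4 × 30 × 3 + 2 × 60 × 30 = 360 + 3600 = 3960.
- Change: (3960 − 5400) / 5400 = −27%. Orders at or above 50/day: 2 before, 2 after.

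**3. The total does respond to each factor.** One order of 60/day × 30 days is 1800. It becomes 1440 (−20%) at 48/day × 30 days, and also 1440 at 60/day × 24 days. The first change crosses the 50/day level and the second does not, yet the outcome is the same.

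**4. Scale.** Taking logs, as section 10 does, changes none of this, because equal totals have equal logs. Dividing by the same number of eligible visits also leaves the equality in step 1 and the 27% in step 2 unchanged. Dividing by the number of opioid orders would change the figures (step 2: 5400/22 = 245 and 3960/6 = 660), but would still apply no threshold.

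**5. The sections side by side.** Section 2.1 restricts its primary outcome to visits at or above 50 mg ME/day and adds an escalation outcome. Section 9.5 tests a decrease for people on high doses. Sections 9.4.1 and 10 use all prescribing, and 9.4.2 adds nothing. These cannot all describe one plan.

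**The case against.** **Total MME contains dose and duration.** A reader might infer that the outcome has no dose or duration component. That is wrong: it is their product, and step 3 shows that it moves with either. The defect is pooling without a threshold.

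**Fewer opioid-naïve orders may themselves be adherence.** A reader might infer that dropping short, low-dose courses lowers MME with no gain in adherence. The documents do not support this. The first recommendation in section 2.1 is to use alternatives to opioids, and under section 5.2 a removed order leads to a prompt for physical therapy and non-opioid options. What stands is narrower: such a fall says nothing about the dose and day limits.

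**Sections 2.2 and 5.2 do not conflict.** Section 2.2 says "Guideline-concordant treatment choices will not require special justification", while section 5.2 says of continuing any opioid-naïve order: "The latter, however, induces a prompt requiring the clinician to justify their decision in free text". A reader might see a contradiction. But the section 2.2 sentence goes on to say that the clinician must opt in to an opioid by giving a justification. The default there is not prescribing, and the opioid-naïve trigger follows it.

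**This is a pilot.** Section 1.1 sets out to "develop and test novel behavioral nudges to encourage adherence to pain and CDC guidelines for opioid prescribing", section 3 makes feasibility the primary aim, and the section 9.1 hypothesis is lower prescribing. Volume is a fair outcome for that hypothesis. No section says that a fall in MME will be reported as adherence, so it goes too far to say that the trial fails its objective. This limits how serious the point is. It does not rescue the sentence, or the mismatch between 2.1, 9.4 and 9.5.

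**Conclusion.** The point holds in a limited form. Weekly MME per clinician is a legitimate volume measure, but it cannot show whether the 50 or 90 mg ME/day levels or the acute-pain day limits in section 2.1 were met. The statement that it captures guideline endpoints is therefore unsupported. For daily dose, the plan also contradicts itself, since outcomes and a hypothesis at high dose are named in 2.1 and 9.5 and absent from 9.4 and section 10. For duration, no outcome exists at all.

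The 900 MME equality and the 27% fall show what can happen. They rest on assumed mixes and on weekly MME being a clinician's weekly total, and they do not estimate what happened in this clinic. The internal mismatch rests on the text alone.

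**What to change.** 1. Delete the sentence at both places in section 9.1 and in section 9.4.1. Describe weekly MME as a measure of prescribing volume.
2. Reconcile 2.1, 9.4 and 9.5. Keep weekly MME as primary and restore the two section 2.1 outcomes in 9.4.2 as secondary: MME at visits with a daily dose of at least 50 mg ME, and the rate of escalation to that dose. Say which hypothesis each serves, and fix the time unit, since 2.1 is monthly and section 10 weekly.
3. Compute them from the ordering data for both 34-week periods, with a clinician random intercept. Use total daily dose per patient, as the long-term trigger does, because concurrent orders add up.
4. Use rates per eligible visit and not shares of orders. In step 2 the share at or above 50/day rises from 2/22 = 9% to 2/6 = 33% although no high-dose order changed. Section 4.1 defines eligible visits for the intervention period only, so state the matching baseline definition.
5. If days' supply is in the extract (assumed; the plan says only ordering data), report the rate of opioid-naïve orders beyond 7 days as a descriptive measure. Note that the section 2.1 figure is for acute pain, while opioid-naïve is defined by prescription history.
6. Base any statement about guideline dose or duration limits on these outcomes and not on total MME. The restored outcomes speak to the 50 mg level only, so make no statement about the 90 mg limit without a count at that level.

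Cost: a few lines in 9.4.2 and section 10, and a few more secondary results to report. No new data collection is needed for the dose outcomes if the extract carries the dose that the trigger already uses.
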